#### \*\*1 cycle equals 21 days

Patients will be treated until progression of disease, unacceptable toxicity, patient or physician choice or study closure. The study will remain open until all patients have discontinued therapy or 1 year from the last enrollee, whichever comes first. If a patient is responding past the timeline listed above, the MSK Principal Investigator may decide to keep the trial open.

Of note, if patient's experiences a greater than 10% change in body weight, dose of romidepsin and carfilzomib should be adjusted accordingly. Doses do not need to be adjusted for less than 10% changes in body weight.

#### Treatment Plan: carfilzomib/romidepsin/lenalidomide Phase Ila

The phase IIa portion is planned to include 20 patients. Each disease cohort, B-and T-cell lymphoma, will have 10 patients. Patients treated at MTD in the phase Ib cohort (if measurable disease at enrollment) will be included towards the 20 patient total in the phase IIa. The MTD has been determined to be dose level 1; 8 mg/m² romidepsin on days 1 and 8, 15 mg lenalidomide from days 1 - 14, and 36 mg/m² carfilzomib on days 1 and 8. The phase IIa cohort will be evaluated both collectively and by disease subtype.

Patients that have received long-term therapy (greater than one year) with response will be allowed to have their schedule modified to allow less frequent dosing per investigator and primary investigator discretion.

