and EFS. ORR is defined as the percentage of patients achieving a best response of CR/Cru or PR at any disease assessment time point. TTR is defined as the time or number of cycles between study registration and documentation of first response (CR/Cru or PR). DOR is defined as the time or number of cycles between documentation of first response and progression, change of therapy, death, or date of last contact (if still alive without progression). EFS is defined as the time between study registration and documented progression, change in therapy, or death if no progression was observed.

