# 9.5.2 Instructions for Dose Modifications or Interruption During Phase 1 Cycle 2 and beyond and phase 2 all cycles

Dose delay and dose reduction rulesare as follows and in the table below. The following dose modification criteria are applicable to adverse events related to study drugs:

- In the event of dose reduction due to toxicity all agents will be reduced as per Table 2, 3, 4. If an agent is already at its lowest dose per tables 2,3,4 then the other agents will be reduced. If the lowest doses are not tolerated the subject will be removed from the study.
- For treatment interruptions during a cycle, the 21-day schedule of each cycle will continue to be followed. Missed doses of lenalidomide, carfilzomib and romidepsin are not made up. For treatment interruptions that delay the scheduled start of a new cycle, when toxicity has resolved as required to allow the start of a new cycle, the restart day of therapy becomes Day 1 of the next cycle.
- If a patient is at the lowest dose level and deriving benefit from therapy, they may continue on protocol therapy despite ≥ grade 3 hematologic toxicity or non-clinically significant non-hematologic toxicity after discussion with the MSK principal investigator. A delay of planned study therapy of greater than 21 days with result in removal from study.

TABLE 2: Lenalidomide Dose Modification Steps		
Current Lenalidomide Dose	One Level Dose Reduction	
20 mg daily on Days 1-14 every 21 days	15 mg daily on Days 1-14 every 21 days	
15 mg daily on Days 1-14 every 21 days	10 mg daily on Days 1-14 every 21 days	
10 mg daily on Days 1-14 every 21 days	5 mg daily on Days 1-14 every 21 days	

TABLE 3: Romidepsin Dose Modification Steps		
Current Romidepsin Dose	One Level Dose Reduction	
10 mg/m  daily on Days 1,8	8 mg/m² daily on Days 1,8	
8 mg/m² daily on Days 1,8	5 mg/m² daily on Days 1,8	
5 mg/m² daily on Days 1,8	5 mg/m² daily on Days 1	
Carfilzomib Dose Modification Steps		
Current Carfilzomib Dose	One Level Dose Reduction	
56 mg/m 	45 mg/m 	
45 mg/m 	36 mg/m 	
36mg/m 	20 mg/m 	

TABLE 4: Dose Modifications for Lenalidomide, Carfilzomib and Romidepsin for Phase 1 cycle 2 and beyond/ Phase 2 all cycles		
NCI CTC Toxicity Grade	Dose Modification Instructions	
, , ,	(also see Instructions for Initiation of a New Cycle above)	

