# 12.1.1 Extracutaneous Response Criteria

Response criteria will be based on assessment following 2 cycles and subsequent assessments will be made every 3 cycles thereafter (e.g. after cycle 5, 8, 11 etc). The criteria are as follows (GTD = Greatest Transverse Diameter; SPD = Sum of the Products of the Greatest Diameter):

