Baseline disease assessments must be performed after discontinuation of most recent anti-cancer therapy including systemic steroids. Outside scans are acceptable if performed within 28 days.

 The imaging modality for evaluation will be dependent on disease subtype. For aggressi ve lymphomas (e.g. DLBCL, PTCL, HL), PET/CT will be used for evaluation of response. For indolent lymphomas, CT alone or PET/CT may be used at the discretion of the treating physician. A bone marrow will only be repeated to confirm a complete response if previously known to be involved. Cutaneous T-cell lymphoma patients (CTCL) will have an mSWAT (Appendix D) performed at these time points and imaging at baseline. In CTCL patient's, imaging will be repeated if appropriate (patients with known nodal or visceral disease) every other cycle. Sezary panel in patients with Sezary syndrome. Cutaneous lymphoma patients without nodal or visceral disease will have imaging repeated only to confirm a complete response.

 An additional safety assessment will be done 28 days (+/- 7 days) following the last dose of protocol therapy.

Response assessment will be performed at the end of cycles 2. Thereafter, response assessment will occur at the end of every third cycle (5.8,11, etc..) until disease progression or removal from study.

10 +/- 3 days

if not performed within 28 days

For cycle 3 and beyond, laboratory assessments performed up to three days prior to the day of treatment are adequate for treatment as long as they are within the treatment parameters.

 For cycles 2, 3 and 4, concomitant medications and adverse events may be performed via an assessment by telephone +/- 3 days of day 15 of the cycle. Beyond cycle 4, day 15 assessments are not required.  5 days to + 3 days.

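### Response assessment follows cycle number rather than calendar time, so cycle-start delays widen the gap in which progression is found, and the two permitted units for TTR and DOR disagree once cycles are not 21 days

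*Combined protocol and SAP*

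**What the plan says.** Section 12.1.1 sets the assessment rule: "Response criteria will be based on assessment following 2 cycles and subsequent assessments will be made every 3 cycles thereafter". Footnote 9 of the study calendar (Appendix G) repeats it: "Thereafter, response assessment will occur at the end of every third cycle". Neither gives an interval in weeks, and the window in footnote 14 is attached to the end of the cycle, so it moves with the cycle. CTCL patients with known nodal or visceral disease have imaging every other cycle where appropriate (footnote 7), which is again cycle-based.

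The treatment plan in section 9.3 states that "1 cycle equals 21 days". Section 9.5.2 separates two kinds of interruption. Doses missed within a cycle leave the 21-day schedule in place. When toxicity delays the start of a cycle, "the restart day of therapy becomes Day 1 of the next cycle", and the patient is removed only if the delay exceeds 21 days.

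The phase IIa treatment plan adds that responders on therapy for more than a year "will be allowed to have their schedule modified to allow less frequent dosing per investigator and primary investigator discretion". It gives no new cycle length and does not mention assessments.

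On endpoints, section 4.2 says "DOR is defined as the time or number of cycles between documentation of first response and progression, change of therapy, death" (or last contact, if alive without progression). TTR has the same choice of unit. EFS is in time only: "EFS is defined as the time between study registration and documented progression, change in therapy, or death if no progression was observed". Section 14.0 plans Kaplan-Meier or competing-risks methods for all three. It does not choose a unit for TTR or DOR and does not address assessment timing.

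**The concern.** Progression enters DOR and EFS on the date it is documented. If the assessment date moves whenever a cycle start moves, patients with dose delays are examined on a wider grid than patients without them. The same would apply to long responders if their modified schedule lengthened the cycle. One Kaplan-Meier curve would then combine patients whose progression was looked for at different intervals, with the difference tied to toxicity.

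The choice of unit is a separate problem. Once a patient's cycles are longer than 21 days, a duration in cycles cannot be converted to the same duration in time. Two analysts following section 4.2 could report different DORs for the same patient. The two effects also pull in opposite directions: late detection tends to lengthen a duration measured in time, whereas counting stretched cycles makes it look shorter.

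**Working it through.** The documents state no precision, power or target for DOR or EFS, so there is no figure of the plan's own to reproduce.

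**Inputs from the documents.** Assessments after cycles 2, 5, 8, 11 and so on (section 12.1.1, Appendix G); 21-day cycles (section 9.3); cycle-start delay of at most 21 days (section 9.5.2); schedule change only after more than one year of therapy with response (phase IIa treatment plan).

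**Assumed inputs.** Cycles of 28 or 42 days under the modified schedule; exponential progression with a median of 26 or 52 weeks.

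**Step 1: assessment gap.** Gap = 3 × cycle length + any cycle-start delays.

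- No delay: 3 × 21 = 63 days (9 weeks).
- One maximal delay in the block: 63 + 21 = 84 days (12 weeks).
- A maximal delay at all three cycle starts: 63 + 3 × 21 = 126 days (18 weeks).
- Modified schedule, doses dropped inside a 21-day cycle: still 63 days (9 weeks).
- Modified schedule, 28-day cycles (assumed): 84 days (12 weeks).
- Modified schedule, 42-day cycles (assumed): 126 days (18 weeks).

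**Step 2: when the one-year rule can act.** 365 / 21 = 17.4 cycles. The neighbouring assessments fall at cycle 17 (17 × 21 = day 357) and cycle 20 (20 × 21 = day 420), so the modified schedule can affect only late follow-up.

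**Step 3: mean lag from progression to the next assessment.** With progression rate λ = ln 2 / median and gap g, mean lag = g / (1 − exp(−λg)) − 1/λ. For the 26-week median, 1/λ = 37.51 weeks; at g = 9, 9 / 0.2133 − 37.51 = 4.68 weeks.

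| Gap | Lag, median 26 wk | Lag, median 52 wk | Added to the 9-week lag |
|---|---|---|---|
| 9 weeks | 4.68 | 4.59 | – |
| 12 weeks | 6.32 | 6.16 | 1.64 and 1.57 |
| 18 weeks | 9.72 | 9.36 | 5.04 and 4.77 |

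The last column is the relevant one, because a lag of about 4.6 to 4.7 weeks is already built into the nominal schedule. After an isolated delay, the added lag applies only to progressions falling inside that one stretched gap.

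**Step 4: effect on an observed median DOR.** Simulation with first response at day 42, 21-day cycles for the first year, then 21-, 28- or 42-day cycles (assumed):

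| True median (months) | Later cycles 21 d | 28 d | 42 d |
|---|---|---|---|
| 8 | 8.3 | 8.3 | 8.3 |
| 12 | 12.4 | 12.9 | 13.8 |
| 17 | 18.6 | 18.4 | 17.9 |

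The median is unchanged, longer or shorter depending on where the assessment dates fall around it. Mean lateness for progressions after one year rises in every case, from about 31 to 42 to 63 days.

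**Step 5: units.** Months = 12 cycles × cycle length / 30.4375. That is 252 / 30.4375 = 8.3 at 21 days, 336 / 30.4375 = 11.0 at 28 days and 504 / 30.4375 = 16.6 at 42 days.

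**The case against.** The strongest objection concerns long responders. A reader might infer that the one-year rule makes progression be looked for less often in exactly these patients, with scans moving to every 12 to 18 weeks and DOR and EFS inflated as a result. The documents do not support that. The phase IIa treatment plan permits less frequent dosing; it does not lengthen the cycle or change assessments. The last romidepsin step in Table 3 already shows less frequent dosing inside the existing schedule (days 1 and 8 become day 1 only). Section 9.3.2 mentions a 28-day cycle only as something a later amendment might explore. This part of the objection stands: what can be criticised is the silence, and the 12- and 18-week figures for these patients are conditional.

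Other limits also stand:

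- A delay moves Day 1 of the next cycle; it does not reset the cycle count.
- Reaching 18 weeks through delays needs the maximum at all three cycle starts, while Table 4 calls for dose reduction after many such toxicities.
- DOR and EFS do not end only at a scan. Death and change of therapy also end them, a physical examination is scheduled on day 1 of each cycle, and unscheduled visits are allowed. The lags above are for progression found only at scheduled assessment.
- Inflation of the median is not guaranteed, as step 4 shows.
- Few patients are involved: 20 in phase IIa, and by default the study closes no later than one year after the last enrolment, although it may be kept open for continuing responders.

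The objection does not remove the delay route, which follows from sections 12.1.1 and 9.5.2 without any assumption about the one-year rule. Nor does it remove the double unit. Kaplan-Meier analysis suggests that time is intended, but section 4.2 still permits either. Late follow-up is also not a remote prospect: section 3.3 cites median response durations of 14.9 and 17 months for romidepsin, and section 3.5 cites responses ongoing beyond a year with romidepsin and lenalidomide.

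**Conclusion.** The point holds in a limited form and is a cheap improvement. As written, one maximal cycle-start delay widens an assessment gap from 9 to 12 weeks, so ascertainment of DOR and EFS depends on dose delays. The added mean lag in detecting progression is about 1.6 weeks for a 12-week gap and about 5 weeks for an 18-week gap, assuming exponential progression with a median of 26 to 52 weeks and detection at scheduled assessments. The direction of any shift in an observed median cannot be stated in advance. For responders beyond one year, the effect ranges from none to an 18-week gap, depending on a cycle length that the plan does not give. The unit conflict in TTR and DOR is present whenever cycles depart from 21 days.

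These are secondary endpoints, described without a comparator or threshold. ORR is little affected, and the DLT stopping rule and sample size are not affected.

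**What to change.** Three changes of wording:

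1. In section 12.1.1 and Appendix G, schedule response assessment by calendar time from cycle 1 day 1: week 6 (2 × 21 = 42 days), then every 9 weeks (3 × 21 = 63 days), with the existing window placed around those dates. State that this applies regardless of dose delays and of any modified schedule after one year.
2. Restate the CTCL nodal or visceral imaging interval in weeks as well: every other cycle is 2 × 21 = 42 days, so every 6 weeks. A general 9-week rule must not overwrite it.
3. In section 4.2, define TTR and DOR in time only and remove the option of counting cycles.

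The cost is that some scans will not coincide with the end of a cycle, and patients on a modified schedule keep the nominal scan frequency. No dose, delay or treatment rule changes.

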# b. Lenalidomide administration

In either phase of the study patients will be asked to take the lenalidomide at approximately the same time each day. If a dose of lenalidomide is missed, it should be taken as soon as possible on the same day. If it is missed for the entire day, it should not be made up. A medication diary will be provided to the patient and asked to be returned prior to each cycle [See Appendix G]. Any pills not used must be returned and all pills must be accounted for.

Patients who take more than the prescribed dose of lenalidomide should be instructed to seek emergency medical care if needed and contact study staff immediately.

# 9.4 Prophylactic Measures

- Subjects should receive prophylactic anti-emetics prior to romidepsin and carfilzomib administration (ondansetron preferred).
- Subjects should receive dexamethasone 4mg PO or IVPB prior to the first two cycles of carfilzomib. Dexamethasone is optional for the subsequent cycles.
- G-CSF may be given at the discretion of the treating physician.
- Subjects should be taking prophylaxis against varicella zoster per the institutional guidelines (e.g. acyclovir 400mg by mouth twice daily) while on this regimen.

#### 9.5 Concomitant Medications

Patients will be instructed not to take any additional medications (including over-the-counter products) during the trial without prior consultation with their treating physician. All medications taken within 30 days of screening and medications and supportive therapies that are administered during the study must be recorded in the electronic Case Report Forms (eCRFs) and in the source documents. Supportive therapy, that is ongoing at baseline, will be permitted during the treatment phase of the study. If other therapy for the disease is required, continuation of the study treatment should be discussed with the MSKPrincipal Investigator. Concomitant medications for other medical conditions are permitted as clinically indicated subject to specific protocol requirements outlined below.

# 9.5.1 Prohibited/monitored concurrent therapy

- Any investigational agent other than lenalidomide or romidepsin.
- Any medications at high risk of causing QTc/QTf prolongation or inducing torsades de pointes (as listed in Appendix E).
- Concomitant use of CYP3A4 inhibitors with romidepsin should be avoided (excluding anti-emetics) to prevent potential increase in romidepsin exposure during concomitant treatment with these drugs. Should a patient already enrolled on this study require treatment with a drug listed in Appendix F romidepsin must be interrupted prior to starting these drugs and should not resume until a washout period of at least 5 half-lives has elapsed.

Any medications that have the potential to alter serum electrolytes (e.g., diuretics) should be monitored very closely for electrolyte abnormalities as these can contribute to the risk of QTc/QTf prolongation and ventricular arrhythmias.

Memorial Sloan Kettering Cancer Center IRB Number: 14-179 A(6) Approval date: 12-Dec-2017

Administrative Update 1: 06-Dec-2018

#### 9.5 **Dose Continuation, Modification and Interruption**

Subjects will be evaluated for AEs at each visit with the NCI CTCAE v4.0 used as a guide for the grading of severity. DLTs as defined will be tabulated in cycle 1 of phase Ib and cycles 1-4 of the phase Ila portion of the study. The toxicity decision rule for the Ila portion is described in Section 14.0. The sections below describe dose reduction steps, instructions for initiation of a new cycle of therapy and dose modifications during a cycle of therapy. Of note, if patient's experiences a greater than 10% change in body weight, dose of romidepsin should be adjusted accordingly. Doses do not need to be adjusted for less than 10% changes in body weight.

# 9.5.1 Instructions for Dose Modifications or Interruption During Phase 1 Cycle 1

There will be no dose reductions in cycle 1 phase 1. Inability to meet treatment criteria will result in holding the dose.

# 9.5.2 Instructions for Dose Modifications or Interruption During Phase 1 Cycle 2 and beyond and phase 2 all cycles

Dose delay and dose reduction rulesare as follows and in the table below. The following dose modification criteria are applicable to adverse events related to study drugs:

- In the event of dose reduction due to toxicity all agents will be reduced as per Table 2, 3, 4. If an agent is already at its lowest dose per tables 2,3,4 then the other agents will be reduced. If the lowest doses are not tolerated the subject will be removed from the study.
- For treatment interruptions during a cycle, the 21-day schedule of each cycle will continue to be followed. Missed doses of lenalidomide, carfilzomib and romidepsin are not made up. For treatment interruptions that delay the scheduled start of a new cycle, when toxicity has resolved as required to allow the start of a new cycle, the restart day of therapy becomes Day 1 of the next cycle.
- If a patient is at the lowest dose level and deriving benefit from therapy, they may continue on protocol therapy despite ≥ grade 3 hematologic toxicity or non-clinically significant non-hematologic toxicity after discussion with the MSK principal investigator. A delay of planned study therapy of greater than 21 days with result in removal from study.

TABLE 2: Lenalidomide Dose Modification Steps		
Current Lenalidomide Dose	One Level Dose Reduction	
20 mg daily on Days 1-14 every 21 days	15 mg daily on Days 1-14 every 21 days	
15 mg daily on Days 1-14 every 21 days	10 mg daily on Days 1-14 every 21 days	
10 mg daily on Days 1-14 every 21 days	5 mg daily on Days 1-14 every 21 days	

TABLE 3: Romidepsin Dose Modification Steps		
Current Romidepsin Dose	One Level Dose Reduction	
10 mg/m  daily on Days 1,8	8 mg/m² daily on Days 1,8	
8 mg/m² daily on Days 1,8	5 mg/m² daily on Days 1,8	
5 mg/m² daily on Days 1,8	5 mg/m² daily on Days 1	
Carfilzomib Dose Modification Steps		
Current Carfilzomib Dose	One Level Dose Reduction	
56 mg/m 	45 mg/m 	
45 mg/m 	36 mg/m 	
36mg/m 	20 mg/m 	

TABLE 4: Dose Modifications for Lenalidomide, Carfilzomib and Romidepsin for Phase 1 cycle 2 and beyond/ Phase 2 all cycles		
NCI CTC Toxicity Grade	Dose Modification Instructions	
, , ,	(also see Instructions for Initiation of a New Cycle above)	

Thrombocytopenia ≥ Grade 3 (platelet count < 50,000/mm³)	
 
If found on the day of romidepsin and/or carfilzomib treatment, hold (interrupt) lenalidomide, carfilzomib and romidepsin dose.
 
Follow CBC at least weekly.
 
Treatment with romidepsin/carfilzomib and lenalidomide may be resumed if thrombocytopenia recovers to ≤ grade 2 thrombocytopenia within 4 days of a planned dose.
 
If thrombocytopenia does not recover to ≤ grade 2 within 4 days, dose is missed and not made up. Reduce one dose level upon resolution of thrombocytopenia to ≤ grade 2.
 
If grade 3 thrombocytopenia found on the days between romidepsin and/or carfilzomib treatment, lenalidomide may be held at the discretion of the treating physician.
 
If grade 4 thrombocytopenia found on the days between romidepsin and/or carfilzomib treatment, hold lenalidomide
 
Follow CBC at least weekly.
 
If thrombocytopenia resolves to ≤ grade 2 prior to Day 14 of the current cycle, lenalidomide may be restarted at the same dose level. Otherwise, omit for remainder of the cycle and reduce the dose of romidepsin, carfilzomib, and lenalidomide by 1 dose level at the start of the next cycle. Omitted doses are not made up.
 
Hold prophylactic anti-coagulation, if applicable.
 
Restart prophylactic anti-coagulation when platelet count is ≥ 50,000/mm³.
 
			
	
 
Platelet transfusion solely to meet treatment criteria are discouraged but may be considered after discussion with the MSK PI.
 
			
Non-blistering rash	If Grade 3, hold (interrupt) lenalidomide, romidepsin and carfilzomib dose. Follow weekly.			
Grade 3 Grade 4	• If the toxicity resolves to ≤ grade 1 prior to Day 14 of the current cycle, restart lenalidomide, carfilzomib and romidepsin at next lower dose level and continue through the scheduled Day 14 of the current cycle. Otherwise, omit for remainder of cycle and reduce the dose of lenalidomide, carfilzomib and lenalidomide by 1 dose level at the start of the next cycle. Omitted doses are not made up.			
	If Grade 4, discontinue lenalidomide, romidepsin and carfilzomib.  Remove patient from study.			
Desquamating (blistering) rash- any Grade	Discontinue lenalidomide, carfilzomib and romidepsin. Remove patient from study.			

TABLE 4: Dose Modifications for Lenalidomide, Carfilzomib and Romidepsin for Phase 1 cycle 2 and beyond/ Phase 2 all cycles				
	Dose Modification Instructions			
NCI CTC Toxicity Grade	(also see Instructions for Initiation of a New Cycle above)			
Neuropathy	
 
If Grade 3, hold (interrupt) romidepsin, lenalidomide and carfilzomib dose. Follow at least weekly.
 
			
Grade 3	• If the toxicity resolves to ≤ grade 1 prior to Day 14 of the current cycle, restart lenalidomide, romidepsin and carfilzomib at next lower dose level and continue through the scheduled Day 14 of the current cycle. Otherwise, omit for remainder of cycle and reduce the dose of lenalidomide, romidepsin and carfilzomib by 1 dose level at the start of the next cycle. Omitted doses are not made up.			
Grade 4	
 
If Grade 4, discontinue lenalidomide and carfilzomib. Remove patient from study. Responding patients may continue on romidepsin off of study.
 
			
Venous thrombosis/embolism ≥ Grade 3	
 
Hold (interrupt) carfilzomib, lenalidomide and romidepsin. Start therapeutic anticoagulation, if appropriate.
 
Restart carfilzomib, lenalidomide and romidepsin at investigator"s discretion after discussion with the MSK PI (reduce 1 dose level of each drug).
 
See Anticoagulation Consideration
 
			
Hyperthyroidism or hypothyroidism	
 
Omit lenalidomide, carfilzomib, and romidepsin for remainder of cy evaluate etiology, and initiate appropriate therapy.
 
See Instructions for Initiation of a new cycle and reduce the dose lenalidomide by 1 dose level.
 
			
Other related non-hematologic toxicity ≥ Grade 3 including grade 3:  • Pulmonary hypertension • Congestive heart failure • Myocardial ischemia • Decreased ventricular function • Hepatic toxicity • Pulmonary complications • Renal Failure	
 
Hold (interrupt) lenalidomide, carfilzomib romidepsin dose. Follow at least weekly.
 
If the toxicity resolves to ≤ grade 2 prior to Day 14 of the current cycle, restart lenalidomide, carfilzomib and romidepsin at one dose level lower and continue through the scheduled Day 21 of the current cycle. Otherwise, omit for remainder of cycle. Omitted doses are not made up. Otherwise, omit for remainder of cycle and reduce the dose of lenalidomide, carfilzomib and romidepsin by 1 dose level at the start of the next cycle.
 
For patients with ≥ grade 3 nausea or vomiting, dose reductions are only required for patients who had persistent ≥grade 3 vomiting despite use of oral and/or IV antiemetics.
 
			

